7.8 Quality Control

By signing this protocol, all parties agree to following applicable standard operating procedures (SOPs). All parties also agree to ensuring all existing and new study personnel are appropriately trained to ensure the study is conducted and data are generated, documented, and reported in compliance with the protocol, Good Pharmacoepidemiology Practice (GPP), and all applicable federal, state, and local laws, rules and regulations. All parties should maintain transparency and open communication in order to effectively manage the study and proactively mitigate any risks.

The study is register-based. As a result, data quality is difficult to ascertain directly. However, previous studies have examined the validity and quality of information in the Nordic registers. The Danish National Prescription Registry contains data of high quality, including detailed information on dispensed drugs, and as the register covers all prescription dispensed in Danish pharmacies, loss to follow-up is unlikely for individuals with permanent residence in Denmark [Kildemoes, H. W., et al 2011]. The completeness of the Norwegian and Swedish prescription registers is characterized as good [Furu, K., et al 2009] [Wettermark, B., et al 2007]. Completeness of registration in the Norwegian prescription

register is ensured by law and quality checks are carried out monthly to identify possible errors or inconsistencies [Furu, K., et al 2009]. The patient identity data are only missing for approximately 0.3% of all items in the Swedish prescription register [Wettermark, B., et al 2007]. The Finnish prescription register has been described in detail and considered as excellent [Klaukka, T. 2001]. Data quality in the Danish National Patient Register is overall assumed to be of high quality; however validity of data depends on the diagnosis under consideration; the positive predictive values for diagnoses similar to those in this study are >90%. [Schmidt, M., et al 2015]. The Norwegian Patient Register has relatively good agreement with the Norwegian Cancer Register [Bakken, I. J., et al 2012] and the completeness and accuracy of the Finnish Patient Register has been evaluated as varying from satisfactory to very good for common diagnoses with positive predictive values ranging from 75%– 99% [Sund, R. 2012]. The validity of the Swedish Patient Register is high for many, but not all diagnoses. The positive predictive values of most diagnoses in the Swedish Patient Register compared to medical records ranges from 85–95% [Ludvigsson, J. F., et al 2011].

The statistical analyses will be performed on servers at Statistics Denmark. The programming will be performed by two researchers independently, limiting programming errors. The statistical programs will be stored on the servers at Statistics Denmark.

The Sponsor may conduct routine or for-cause audits to ensure oversight and conduct of the study are completed in accordance with the protocol, quality standards (e.g. GPP), and applicable laws and regulations. If a significant quality issue (SQI) is identified at any time during the conduct of the study, it must be escalated to the Sponsor immediately. A SQI is any issue with the potential to negatively impact, either directly or indirectly, the rights, safety and well-being of patients or study participants and/or the integrity of the data. In the event an audit or SQI results in corrective or preventive actions, all parties are expected to appropriately implement the action plan in a timely manner.

7.9 Limitations of the research methods

The present study utilizes observational data from nationwide population registers covering the entire population meaning the total population is included and that loss to follow-up is minimal, limiting the impact of selection bias on results. Furthermore, observational data are extracted from health registers which are established and operated for purposes not immediately related to the present study. This minimizes information bias related to the differential misclassification of outcomes, but introduces other types of limitations with respect to quantifying exposure, outcome, and confounders as outlined below:

Exposure: Use of DL

- The prescription registers capture information on purchasing of drugs from pharmacies. The actual adherence of prescribed drugs and consumption cannot be established in these databases. This is a major limitation because the drugs concerned are taken on an as needed basis to treat symptomatic disease. Thus, it is difficult to establish when persons are truly exposed to the drug. Therefore, supplementary analyses will be performed to characterize the relationship of prescribing and timing of events of interest by categorizing time since DL prescription to the outcomes of interest and by using 52 instead of 26 weeks beyond previous prescription redemption as start of an unexposed period.
- Left-truncation is a potential bias in the study meaning that we have no information on DL use before the start of registration of prescriptions in each country. Left-truncation bias in relation to DL use is only a relevant issue for Sweden and Norway since DL was available from 2001, but the prescription registers in Norway and Sweden were established in 2004 and 2005, respectively (Table 4). Therefore, we do not know whether a DL user in the first year of registration in Norway and Sweden is a long-term user (prevalent user) or a first-time user (incident user). To account for this potential bias, a person with prescription redemption of DL in Norway and Sweden within the first 6 months after establishment of the prescriptions registers will not be included. This is not a limitation in Denmark and Finland since DL was first approved in 2001 and the prescription registers in Denmark and Finland were established in 1995 and 1994, respectively. However, left-truncation bias might also occur when persons are immigrating into the study population. Therefore we also exclude persons with DL prescription redemptions within 6 months after immigrating to Denmark, Finland, Norway, or Sweden.
- There is a possibility that patients could purchase DL over-the-counter; however, because of reimbursement systems in the Nordic countries, it is actually less expensive to purchase prescription DL. In Norway and Sweden DL has only been allowed for prescription sale; However, in Denmark, DL has been available for over-the-counter sale since 2013, but over-the-counter sales only counted for less than 4 % of the total amount of DL purchased in 2013. A supplementary analysis will examine the associations under consideration restricting the time period to include only years where DL was not allowed for OTC sale.
- Loratadine, the parent compound of DL, is also available via prescription and over-the counter in the Nordic countries. We think it is somewhat unlikely that patients would switch between DL and loratadine. However, it is possible that some of the time counted as unexposed in the analyses could actually be time exposed to loratadine or over-the-counter DL. Moreover, other non-sedating prescription antihistamines are available in the Nordic countries, and if the effect on the outcomes

is driven by non-sedating prescription antihistamines in general, rather than the specific effect of desloratadine exposure only, these drugs should be examined to elucidate potential misclassification of exposure. To explore exposure misclassification (i.e., the influence of loratadine and other non-sedating prescription antihistamines on the associations under study), we will conduct supplementary analyses, which will be specified in the statistical analysis plan.

Outcome: Episodes of seizures, SVT, and A-fib/flu

- Seizures, SVT, or A-fib/flu not registered with a relevant diagnosis code in the national patient registers will not be included in the study. However, the completeness of registration is assumed high, since both a procedure for data control of information in the national patient registers is established, and hospitals have an incentive to register patients, as the financing of hospitals is based on the registration of patients treated and procedures performed. If under-recording exists, it would reduce the number of outcomes evaluated, but this under-recording is not likely to be differential (i.e. associated with periods of use or nonuse of DL) and introduce bias.
- The coverage of calendar years in the national patient registers differ between the Nordic countries and may be insufficient to capture the complete history of seizures, SVT, or A-fib/flu at the individual level. Regarding seizures, recurrent seizures would be studied as primary seizures, if first seizure happened before start of registration.
- Truncation is a potential bias in the study meaning that we have no information on seizures, SVT, and A-fib/flu before the start of registration of each of these variables. For Denmark, Finland, and Sweden, information on seizures, SVT, and A-fib/flu is available from 1977, 1967, and 1987, respectively. Thus, the impact of truncation bias on results from these countries is limited. However, information on seizures, SVT, and A-fib/flu in Norway is only available from 2008, which limits the study period of the Norwegian data further and increases the risk of truncation bias.
- The present study aims at studying incident outcomes occurring in the community setting. To differentiate between incident and prevalent disease, we exclude persons with registered disease before baseline. In addition, we used surrogates of prevalence (i.e., redeemed prescriptions of antiepileptic medicine) to exclude persons with prevalent disease. To capture disease cases emerging in the community setting, we limit ascertainment to those sites of care where incident presentation would be present and use only primary diagnoses of hospitalization, as secondary diagnoses often represent conditions emerging during hospitalization.

Confounders

In the present study, we expect complete information on the central confounders of age, sex, calendar year, country, and seasonality, as these are measured as key variables in the registers and information on these variables has to be entered into the system to establish a record file.

Information on the three confounders of severity of rhinitis, asthmatic status, and chronic urticaria status is challenging to obtain from the nationwide registers for many reasons. First of all, these conditions in general emerge in the primary health care sector where patients normally seek care from their general practitioner for treatment of symptoms. Second, truncation bias may, as with regard to the measures of exposure and outcome, also occur in relation to these three confounders in Norway as the patient register was established in 2008, making the follow-up period rather short. Third, different issues regarding codes and use of drugs for the three conditions have to be realized and discussed to understand the potential impact of residual confounders in the present study. We have discussed these issues with clinical experts and the essence of the discussion is given below.

- Severity of rhinitis is measured as use of immunotherapy and the binary measure of severity of rhinitis will not capture different levels of disease severity. Therefore, we expect the sensitivity of the measure to be rather low and severity of rhinitis to be underreported in the present study. However, we do not expect misclassification of those persons who received immunotherapy, as it is assumed that persons receiving immunotherapy also have severe rhinitis. A quantitative bias analysis examining the impact of misclassification of severity of rhinitis on the results will be performed.
- Identifying persons with asthma by use of register data is challenging due to the fact that the drugs used for treatment of asthma overlap with the treatment of chronic obstructive pulmonary disease (COPD). In order not to misclassify persons with COPD into the group of persons with asthma, we identify persons with asthma as those initiating asthma treatment before the age of 45 years. However, this means that for the part of the population aged 45 years or older, we will only have information on asthmatic status from the patient register in which hospitalized cases are registered. These cases are more likely to have severe asthma than those identified through the prescription register meaning that residual confounders may be more likely to occur among the population older than 45 years than those younger. A quantitative bias analysis examining the impact of misclassification of asthma on the results will be performed.

- Chronic urticaria is a very rare diagnosis given at highly specialized hospital units. This means that we expect a delay from onset of symptoms of chronic urticaria and the diagnosis of chronic urticaria of approximately 2-5 years. In the period between onset of disease and diagnosis, persons may receive antihistamines, including DL prescribed by the general practitioner, for their symptoms. Therefore, chronic urticaria may be underreported in the hospital register and the sensitivity of the measure is expected to be somewhat low. To get an impression of how important this misclassification will be in the present study, we will look at how many of the persons with a diagnosis of chronic urticaria have redeemed prescriptions of DL during the five years prior to the date of diagnosis. A quantitative bias analysis examining the impact of misclassification of chronic urticaria on the results will be performed.
- As in any association study, there is always the possibility of unmeasured confounders or residual confounding resulting from roughly categorized confounders that could affect the results of the study.

Variables used for inclusion and exclusion criteria

In Substudy 2B, seizure outcomes for which a drug overdose is also registered at the same hospitalization are excluded. In general, drug overdoses are likely to be underreported in the registries, as the registries often do not have sufficient detail to differentiate between overdoses from different types of drugs. Therefore, it is not possible to distinguish between overdoses from DL and overdoses from other drugs. Because overdoses of DL are rare compared to other drug overdoses, persons with any drug overdose registered during the same hospitalization as the seizure are excluded from analysis 2B. As a result, this study cannot determine whether the seizure outcomes are specifically associated with DL overdoses.

Sample size

Based on the assumptions made, the sample size is not adequate in the youngest age group for the assessment of the potential association between DL use and A-fib. Also, in this age group only relatively strong associations (IRR=8.2) can be properly assessed for the association between DL use and SVT.

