7.3.2 Outcomes

Three outcome variables will be used in the present study: first seizure (Substudy 2B), first SVT (Substudy 3B), and first A-fib/flu (Substudy 4B). Except where noted, the case definition of seizure excludes febrile seizure, a condition in infancy and early childhood attributed to fever. However, supplementary analysis 2 will evaluate the outcomes of febrile and non-febrile seizures in children. (The diagnosis of febrile seizure is generally not used in adults.) Information on outcome variables will be obtained from the Nordic national patient registers, including diagnostic and treatment information for patients treated at the secondary and tertiary hospital level in all four Nordic countries using International Classification of Diseases (ICD)- 10 codes. We will exclude seizure cases if they are registered with brain tumor (benign and malignant), stroke, or acute drug intoxication or overdose of drugs during the same hospitalization as the seizure. [Table 2](#) gives an overview of the outcome variables in the study. For all outcome variables, we will include the primary diagnoses from the emergency room or inpatient settings registered in the Nordic national patient registers.

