Diabetes (both type 1 and type 2)	Yes	Yes	Yes	No	No	No
Use of hypoglycemic agents (oral anti-diabetics, insulin)	Yes	No	No	No	No	No
Hypertension	No	Yes	Yes	No	No	No
Thyroidism (both hypo- and hyperthyroidism, e.g., Grave's disease, thyrotoxicosis)	No	Yes	Yes	No	No	No
Structural heart disease: Left ventricular hypertrophy, left ventricular systolic dysfunction, chronic heart failure (CHF)	No	Yes	Yes	No	No	No
Seasonality (i.e., winter [December-February], spring [March – May], summer [June-August], and autumn [September-November])	Yes	Yes	Yes	Yes	Yes	Yes

Potential confounding factors	Potential confounder included in the DAG			Confounders included in the selected minimum sufficient adjustment set for each association study		
	Seizures	SVT	A-fib/flu	Seizures	SVT	A-fib/flu
Asthmatic status	Yes	Yes	Yes	Yes	Yes	Yes
Disease severity of rhinitis	Yes	Yes	Yes	Yes	Yes	Yes
Chronic obstructive pulmonary disease (COPD)	Yes	Yes	Yes	No	No	No
Smoking	Yes	Yes	Yes	No	No	No
Inflammatory disease	No	Yes	Yes	No	No	No
Metastatic disease	Yes	No	No	No	No	No
Infections	No	Yes	Yes	No	No	No
Stroke	Yes	Yes	Yes	No	No	No
Chronic urticaria	Yes	Yes	Yes	Yes	Yes	Yes
Unspecific autoimmune disease	Yes	Yes	Yes	No	No	No
Type 1 allergy	Yes	Yes	Yes	No	No	No
Antihypertensive treatment	No	Yes	Yes	No	No	No

Table 4 below shows the variables included in the minimum sufficient adjustment sets in all four association analyses. In addition to being confounders included in the association analyses, the variables in the minimum sufficient adjustment sets will be used to characterize the population using DL in the descriptive study of DL use (Substudy 1). The table describes how each of the variables will be operationalized. ICD-10 codes and ATC codes that will be used for the definition of the variables can be found in Annex 6.

Table 4 Definition of confounders included in the minimum sufficient adjustment sets that will be used for confounder adjustment in the association studies.

Confounders included in the minimum sufficient adjustment sets	Definition	Data source

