7.4 Data Sources

The DL study will include register information from four Nordic countries – Denmark, Finland, Norway, and Sweden. In addition to a long history of collecting high quality information on births, deaths, immigration and emigration, disease incidence, and activities in the healthcare sector [Thygesen, L., et al 2011], exceptional opportunities to perform register-based research are driven by the unique PIC introduced in the Nordic countries in the 1960's and available to all persons with permanent residence in the Nordic countries [Pedersen, C. B. 2011]. The PIC makes it possible to link information at the individual level from several registers for scientific research purposes. The national prescription registers and national patient registers within each of the Nordic countries capture all the individual encounters of purchasing prescribed DL and allow sufficient longitudinal data to differentiate between first and recurrent seizures, as only first seizure will be analyzed, and to identify incident SVT and A-fib/flu cases. Person-specific use of DL will be elucidated from the

national prescription registers by obtaining information on redemption of DL prescription for each person [Furu, K., et al 2009]. Person-specific information on seizures, SVT, and A-fib/flu will be derived from the Nordic national patient registers.

Table 5 presents key information on the population-based health registers in the Nordic countries of relevance for the present study. Data will be available until and including 2015 for all countries. The data extraction period refers to the longest period for which data on exclusion variables (e.g., seizures, SVT, or A-fib/flu before baseline) can be obtained for.

Table 5 Overview of national health registers in the Nordic countries of relevance for the present study.

Register	Country			
	Denmark	Finland	Norway	Sweden
National prescription register	1995–2015	1994–2015	2004–2015	2005–2015
National patient register	1977–2015 (1)	1967–2015 (2)	2008–2015	1987–2015 (3)
Civil registration system	1968–2015	1967–2015	1964–2015	1965–2015
Study period	2001–2015 (15 years)	2001–2015 (15 years)	2008–2015 (8 years)	July 2005–2015 (11 years)
Data extraction period	1977–2015	1967–2015	2008–2015	1987–2015

(1) Contacts with outpatient clinics (incl. emergency departments) since 1995.

(2) Contacts with outpatient clinics (incl. emergency departments) since 1998.

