12.6 Annex 6 ICD-10 Codes and ATC Codes

Diagnosis/drugs to be identified in registers	Proposed classification system	Proposed codes by clinicians
Acute drug intoxication and overdose of drugs	ICD-10	T88.6 T88.7 T36 T50
Antiepileptic medicine	ATC	N03A N05BA
Asthma	ICD-10	J45
	ATC	R03A and R03B
Atrial fibrillation or flutter	ICD-10	I48
Brain Tumor (both malignant and benign)	ICD-10	C70 and C71 D33
Chronic urticaria	ICD-10	L50 (excluding acute urticaria: L50.8D) L56.3
Congenital pre-excitation syndrome	ICD-10	I45.6
Desloratadine	ATC	R06AX27
Epilepsy	ICD-10	G40
Head trauma	ICD-10	S06
Loratadine	ATC	R06AX13
Malignant brain tumor	ICD-10	C70 and C71
Seizure	ICD-10	R56
Severe rhinitis (immunotherapy)	ATC	V01AA (excluding V01AA07)
Stroke (all types)	ICD-10	I61 I62 I63 I64.9
Supraventricular arrhythmias	ICD-10	I47.1

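### Annex 6 gives the exclusion diagnoses in ICD-10 only, so part of the look-back from 1977, 1967 and 1987 that 7.9 relies on cannot be searched

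*Protocol*

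**What the plan says.** All three outcomes are incident. Section 7.2.2 removes persons with earlier disease: seizure, epilepsy, antiepileptic prescriptions, malignant brain tumour or head trauma for 2A and 2B, and SVT, A-fib/flu or congenital pre-excitation for 3A-4B.

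Table 5 in 7.4 gives data extraction periods from 1977 (Denmark), 1967 (Finland) and 1987 (Sweden). The text above it explains what they are for: "The data extraction period refers to the longest period for which data on exclusion variables" can be obtained. Section 7.9 repeats the years ("For Denmark, Finland, and Sweden, information on seizures, SVT, and A-fib/flu is available from 1977, 1967, and 1987, respectively") and concludes: "Thus, the impact of truncation bias on results from these countries is limited".

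The codes stand in "12.6 Annex 6 ICD-10 Codes and ATC Codes". The relevant rows are seizure R56, epilepsy G40, SVT I47.1, A-fib/flu I48, pre-excitation I45.6, head trauma S06 and malignant brain tumour C70/C71. All are ICD-10. No earlier revision, mapping or recoding is mentioned in the protocol.

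Section 7.9 does concede that disease history may be incomplete, but it ties this to years before registration began. It treats every registered year as usable.

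**The concern.** The length of a look-back is set by the years in which the listed codes can find a record, not by the years in which a register exists. If the exclusions are programmed from Annex 6 as it stands, register years before ICD-10 adoption contribute nobody, although Table 5 and 7.9 count them as history.

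New-onset status is then at stake. A person whose only registered arrhythmia or seizure falls in those years passes the screen, and a recurrence during follow-up is recorded as a first event. The general-population incidence rates (2A-4A) are primary objectives and would be raised by such events. The usable look-back grows with calendar time, so the early study years are the most exposed. Section 7.9 says that Norway's short history raises the risk of truncation. The same reasoning applies wherever the effective history is shorter than stated.

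**Working it through.** **Inputs from the protocol**
- Start of diagnosis history: Denmark 1977, Finland 1967, Sweden 1987 (7.9). Table 5 gives the same years, so the stated figures agree with each other.
- Start of study period: 2001 for Denmark and Finland, July 2005 for Sweden (7.2, Table 5).
- Start of prescription registers: Denmark 1995, Finland 1994, Sweden 2005 (Table 5).

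**Assumption.** The first ICD-10 year in each register is not in the documents. I vary it from 1990 to 1998, counted from 1 January, and assume that older records were not recoded.

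**Look-back at study start** = study start minus history start:
- Denmark 2001 − 1977 = 24 years
- Finland 2001 − 1967 = 34 years
- Sweden 2005.5 − 1987 = 18.5 years

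**Unsearchable share** = (first ICD-10 year − history start) / look-back:

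| First ICD-10 year | Denmark | Finland | Sweden |
|---|---|---|---|
| 1990 | 13/24 = 54% | 23/34 = 68% | 3/18.5 = 16% |
| 1994 | 17/24 = 71% | 27/34 = 79% | 7/18.5 = 38% |
| 1998 | 21/24 = 88% | 31/34 = 91% | 11/18.5 = 59% |

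**Break-even.** More than half of the look-back is lost if adoption falls after the midpoint of the interval:
- Denmark (1977 + 2001)/2 = 1989
- Finland (1967 + 2001)/2 = 1984
- Sweden (1987 + 2005.5)/2 = 1996.25

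So at study start the larger part is lost in Denmark and Finland over the whole assumed range. In Sweden this holds only for its last years.

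**Later entrants.** For a person entering on 1 January 2015 the look-back is 38, 48 and 28 years. The shares over the same range are:
- Denmark 13/38 to 21/38 = 34-55%
- Finland 23/48 to 31/48 = 48-65%
- Sweden 3/28 to 11/28 = 11-39%

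**Second screen for seizure.** In 2A and 2B, antiepileptic prescriptions also exclude (7.2.2; ATC N03A and N05BA in Annex 6). At study start this adds 2001 − 1995 = 6 years in Denmark, 2001 − 1994 = 7 in Finland and at most about half a year in Sweden. For SVT and A-fib/flu, 7.2.2 names no drug-based screen.

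**The case against.** - **Seizure has a second screen.** A reader might infer that all prevalent disease is screened by ICD-10 alone. That is not so: the antiepileptic-prescription exclusion works independently of diagnosis codes. This stands, and it moves the weight of the point to SVT and A-fib/flu.
- **Other ICD-10 statements do not govern the exclusion history.** In 7.3.2, "using International Classification of Diseases (ICD)- 10 codes" describes how outcomes are identified. In 7.3.3, "ICD-10 codes and ATC codes that will be used for the definition of the variables can be found in Annex 6" refers to the Table 4 confounders, whose diagnosis-based definitions use a five-year window. This is correct, so the point rests on Annex 6. But Annex 6 has rows for epilepsy and pre-excitation, which the association analyses use only as exclusions, so the list is meant to cover exclusions too.
- **Mapping may be left to the SAP or to programming.** The SAP is not shown. Section 7.6 has the coordinators build populations that include years before the study period, and the data control report must describe known misclassification. Annex 6 also labels its codes as proposed. Codes valid in those years may therefore have been intended. This is possible, but the conclusion in 7.9 is the protocol's own, and its code list does not support it.
- **Empty years are not misclassified persons.** A reader might infer from the shares that old disease is generally counted as new. The documents do not support that. A person is affected only with no ICD-10-coded contact before entry (and, for seizure, no antiepileptic prescription), followed by a qualifying primary diagnosis. No number is available. Many users are also young: (20,000 + 86,000) / 365,500 = 29% of the annual users in 7.5.1 are under 20 and have little or no life before ICD-10. This stands in full.
- **The main comparison may be little affected.** Substudies 2B-4B compare exposed with unexposed time among desloratadine users, a design chosen to reduce confounding by fixed characteristics. No direction or size of bias in the rate ratios has been shown.

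**Conclusion.** The point holds as an inconsistency between the code list and a stated conclusion. Annex 6 as written cannot search the register years that Table 5 and 7.9 count as history, so the judgement that truncation matters little in Denmark, Finland and Sweden does not follow.

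Under the assumed adoption range of 1990-1998, 54-88%, 68-91% and 16-59% of the look-back at study start is unsearchable in the three countries in that order, falling to 34-55%, 48-65% and 11-39% for entry in 2015. These figures rest on the assumed year and on older records not having been recoded. They measure lost years, not persons.

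The likely consequence is that some persons with old disease count as first events. This applies mainly to SVT and A-fib/flu and to the early-year rates of 2A-4A. Seizure is partly protected, least so in Sweden. A reader might go further and conclude that the 2B-4B rate ratios are biased, but the documents give no basis for a direction or size.

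**What to change.** Add to Annex 6, for every exclusion diagnosis in 7.2.2, the equivalent codes of the earlier ICD revisions used in each register, and apply them to the register years in Table 5. Where a diagnosis cannot be mapped, state the effective look-back per country in Table 5 and revise the conclusion on truncation in 7.9 to match.

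The cost is a longer code list and reprogrammed exclusions. Table 5 already plans extraction back to these years. If national datasets were in fact drawn with ICD-10 codes only, the earlier cases would have to be extracted as well. Earlier codes may be less specific, for example for SVT, so some persons may be excluded wrongly. Section 5 says that the methods repeat P203 apart from dropping the secondary analyses. If the exclusions change for the three countries already reported, the loss of comparability with P203 should be noted. Restating the look-back and revising 7.9 alone costs only text.
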